In a prospective study, Gaba et al.¹¹ compared 50 aneurysms treated primarily with Hydrocoil (mean 71.8% based on coil length) to 57 volume- and shape-matched aneurysms embolized with bare platinum coils. The overall recurrence rate of the Hydrocoil treated aneurysms was 17% and compared favorably to those treated with bare platinum coils (24%) during a mean follow-up period of 12.3 months. These results also compare favorably to those reported by Murayama et al.¹² from their 11 year experience with bare platinum coils where the overall recanalization rate was 20.9%. Geyik et al.¹³ studied the recurrence rate in 35 bifurcation aneurysms, known for a higher tendency for recurrence, when treated with Hydrocoil and demonstrated an initial complete occlusion rate of 82.9% and at 6 months follow-up the overall recanalization rate was 11.4%.

Several other studies have examined hydrogel coils and the rates of initial complete occlusion have varied between 28% to 75% with recurrence rates between 11% and 28.1%.^{14,15} Tables 1 and 2 summarize the most relevant papers and their findings on occlusion rates, recanalization, retreatment, complications, morbidity and mortality rates. As a point of reference, the overall retreatment rate in the International Subarachnoid Aneurysm Trial (ISAT) was 17.4%, with an early retreatment rate of 8.8% and a late retreatment rate of 9.0%.¹⁶ The cut-off point between early and late retreatment was 3 months.¹⁶

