9.1 Sample Size Estimation

For univariate associations, using a two-sided two-sample test of proportions (Chi-square test), Table 5 shows the effect sizes one would be able to detect for given baseline rates (assuming 1:1 randomization and 5% type I error rate) at 80% power.

Using multiple logistic regression to predict recurrence (baseline rate in Platinum group of 33%), the sample of 600 patients would provide 80% power to detect an odds ratio between 0.60 and 0.47, depending on the r-squared of the other covariates to coils (between 0-0.2; note r-squared of 0 corresponds to hydrogel rate of 22.8% as in the univariate analysis). Likewise, for complete occlusion (baseline rate of .556), a sample of 600 provides 80% power to detect odds ratios between 1.60-1.70, depending on the r-squared of the other covariates to coils (between 0-0.2; note r-squared of 0 corresponds to hydrogel rate of .678 as above). Similarly, for recanalization, one would have 80% power to detect odds ratios between 0.613-0.577 (n=600).

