¹ For Subjects enrolled with ruptured aneurysms² According to standard of care of each institution.³ For Subjects with ruptured aneurysms who are unable to complete the SF-36 prior to procedure, the SF-36 can be completed prior to subject discharge following procedure.

Table 5. Effect Sizes for outcomes with N=600, with 80% power

Outcome	baseline (platinum) rates	Hydrocoil rates	% change
Recurrence	33.0%	22.8%	-30.9%
Complete occlusion	55.6%	66.7%	20%
	47.6%	59.0%	23.9%
Complete or nearly complete occlusion	85.5%	92.6%	8.4%
Retreatment	17.4%	9.6%	-44.8%

Table 6. Electronic Data Entry Timelines

eCRF	Timeline
Adverse Event eCRF	
In the event of a serious adverse event, complete the AE CRF on the web-based database and fax report within 24 hours of learning of the event to the Sponsor and Funder. Comply with local reviewing IRB reporting rules.
 
In the event of an unanticipated adverse device effect, complete the AE CRF on the web-based database and fax report as soon as possible, but no later than 10 working days after the investigator first learns of the effect to the Sponsor and Funder. Comply with local reviewing IRB reporting rules.

All other eCRFs	Within 5 business days of subject discharge or follow-up

Table 7: Required Imaging Schedule

HydroCoil Embolic System Clinical Trial	Screening & Baseline	Surgery		Post-Procedure Follow-up	Immediate Follow-up	Early Follow-up	Final Follow-up
		Pre-Coil	Post-Coil				
Schedule of Events	Up to 30 days prior to surgery			Day 1	3-28 Days	3-12 Months	18-24 Months
Angiogram		X	X			X	X
MRA						X ²	X ²

² According to standard of care at each institution

Please note that if an angiogram, MRA or CTA is performed 30 days before surgery, the Imaging eCRF should be completed and the CD shipped to the core lab and Northwestern University. This imaging is optional and is not required for the study.

Results of MRIs or CTs are not needed

Figure 1. Aneurysm occlusion grading system as reported by Meyers et al.²³

[figure not shown]

Figure 2. Raymond angiographic classification of residual coiled aneurysm.

[figure not shown]

Figure 3: Classification of Adverse Events

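### Section 9.1: two detectable effects do not follow from the stated inputs (0.47 for recurrence, .678 for complete occlusion), and the recanalization power claim gives no baseline rate

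*Combined protocol and SAP*

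**What the plan says.** Section 9.1 bases the univariate calculations on a "two-sided two-sample test of proportions (Chi-square test"), "assuming 1:1 randomization and 5% type I error rate", with 80% power. Table 5, titled "Effect Sizes for outcomes with N=600, with 80% power", lists the detectable rates. A second paragraph in section 9.1 turns to multiple logistic regression and gives three ranges of detectable odds ratios:

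- **Recurrence (primary endpoint), platinum rate 33%:** "80% power to detect an odds ratio between 0.60 and 0.47", the range "depending on the r-squared of the other covariates to coils (between 0-0.2; note r-squared of 0 corresponds to hydrogel rate of 22.8"%.
- **Complete occlusion, platinum rate .556:** odds ratios 1.60 to 1.70 over the same r-squared range, with the remark "note r-squared of 0 corresponds to hydrogel rate of .678 as above". Table 5 pairs 55.6% with 66.7%.
- **Recanalization:** "for recanalization, one would have 80% power to detect odds ratios between 0.613-0.577 (n=600"). No platinum rate is given.

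Section 9.2.2 lists recanalization among the binary secondary outcomes to be analysed, and the hypothesis in section 4.1 names it. Section 4.3 does not list it under that name, and section 6.4 uses recanalization and recurrence together without separating them. The one platinum rate labelled recanalization is in section 3.5, for an 11-year series "where the overall recanalization rate was 20.9"%.

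**The concern.** An odds ratio and a sample size do not fix the power for a binary outcome; the control-arm rate is needed too. For recanalization it is missing, so the 80% cannot be checked. If the true platinum rate is near those cited in the background, the power for that effect is well below 80%, and a non-significant recanalization result could be read as stronger evidence against an effect than it is.

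The other two figures have all their inputs stated and still do not reproduce. One concerns the primary endpoint. A reader relying on 0.47 would think that covariate adjustment costs far more sensitivity than an r-squared of 0.2 implies.

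**Working it through.** **Inputs (section 9.1 and Table 5).** Two-sided alpha 0.05, 1:1 allocation, N = 600 (300 per arm), r-squared 0 to 0.2. For recanalization the r-squared range is carried over from the two preceding sentences. All 600 are taken as evaluable, as the plan does.

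**Formulas.** For a platinum rate p1 and odds ratio OR, the hydrogel rate is p2 = OR·p1/(1 − p1 + OR·p1). With p̄ = (p1 + p2)/2,

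power = Φ{ [ |p1 − p2|·√n − 1.96·√(2p̄(1 − p̄)) ] / √(p1(1 − p1) + p2(1 − p2)) }.

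Here n = 300·(1 − r-squared) per arm: 300 at r-squared 0 and 240 at 0.2.

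**Step 1: reproduce the plan's figures.** For 33.0% against 22.8%, the numerator is 0.102·√300 − 1.96·√0.4023 = 1.767 − 1.243 = 0.524 and the denominator is 0.630. Power is Φ(0.83) = 79.7%, and the odds ratio is 0.600. For complete occlusion at 55.6%, the odds ratios detectable with 80% power are 1.601 (r-squared 0) and 1.697 (r-squared 0.2), matching the stated 1.60 to 1.70. The method therefore agrees with the plan's.

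**Step 2: recurrence at r-squared 0.2.** At p1 = 33% and n = 240:

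- OR 0.47 gives p2 = 18.8% and power 94.7%.
- OR 0.56 gives p2 = 21.6% and power 80.1%.

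Reaching only 80% power at 0.47 would need about 148 per arm, so r-squared would be 1 − 148/300, about 0.5.

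The plan's own ranges show the same thing. An r-squared of 0.2 should stretch the log odds ratio by about √(1/0.8) = 1.118:

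| Outcome | Stated range | Ratio of log odds ratios |
|---|---|---|
| Complete occlusion | 1.60 to 1.70 | 1.13 |
| Recanalization | 0.613 to 0.577 | 1.12 |
| Recurrence | 0.60 to 0.47 | 1.48 |

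**Step 3: complete occlusion.** The platinum odds are 0.556/0.444 = 1.252.

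- 66.7%: (0.667/0.333)/1.252 = 1.60, power 79.8%.
- 67.8%: (0.678/0.322)/1.252 = 1.68, power 86.9%.

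Only 66.7% fits both Table 5 and the odds ratio of 1.60 at r-squared 0.

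**Step 4: recanalization.** Solving for the platinum rate at which power is 80% gives 38.2% for OR 0.613 at r-squared 0, and 38.4% for OR 0.577 at r-squared 0.2. Each equation has a second root, at 72.5% and 73.6%; between the roots power exceeds 80%. At the platinum recurrence and recanalization rates in the available text:

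| Platinum rate | Source | Power at OR 0.613, r-squared 0 | Odds ratio detectable at 80%, r-squared 0 to 0.2 |
|---|---|---|---|
| 20.9% | 11-year platinum series, section 3.5 | 61.4% | 0.536 to 0.492 |
| 24% | matched platinum group, section 3.5 | 66.3% | 0.557 to 0.515 |
| 29% | last coil platinum, section 3.5 | 72.5% | 0.583 to 0.544 |
| 33% | design rate for recurrence, section 9.1 | 76.3% | 0.598 to 0.560 |

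At OR 0.577 with r-squared 0.2, power is within about 0.6 points of the third column in every row.

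**The case against.** The strongest reply is that a missing input is not a shortfall. The plan ties the recanalization odds ratios to no baseline, and the lower rates in the table come from other series with their own follow-up; the plan does not adopt them for recanalization. At its own 33% the gap is under 4 points. If 33% is taken as the event rate over both arms combined, the platinum rate becomes 38.4% for OR 0.613 and 39.0% for OR 0.577, and power is 80.1% and 80.4%. The figure may therefore rest on a different convention for 33%. That is plausible, but section 9.1 defines 33% as the platinum-arm rate.

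Three stronger readings are tempting, and the documents do not support them:

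- **That 80% power holds only near 38%.** It holds from about 38% to about 73%.
- **That the claim fails at every platinum rate in the protocol.** The complete-occlusion baselines in Table 5 (47.6% and 55.6%) give 83.8% and 84.8%. They belong to another outcome, so the statement must be limited to recurrence and recanalization rates.
- **That the trial lacks its stated power.** No baseline is committed to for recanalization, and the introductory text before section 3.1 was not available, so the absence of a rate near 38% is confirmed only for the rest.

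It is also fair to say that the practical harm is small. Recanalization is secondary, and section 9.2 commits to odds ratios with 95% confidence intervals, from which a null result would be read. None of this rescues 0.47 or .678, whose inputs are all stated.

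**Conclusion.** The point holds as a correction to the text of section 9.1.

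1. **Recurrence, primary endpoint.** The limit of 0.47 is wrong on the plan's own inputs; about 0.56 is right.
2. **Complete occlusion.** The .678 contradicts Table 5 and the odds ratio in its own sentence; .667 is consistent with both.
3. **Recanalization.** The 80% claim cannot be verified without a baseline. It implies a platinum rate of at least about 38%, against power of 61% to 76% at the cited rates of 20.9% to 33%. If recanalization is the same as recurrence, 0.613 conflicts with the 0.60 given earlier in the same paragraph.

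The errors run in different directions: the first two understate the trial's sensitivity, and the third may overstate it. The results rest on the pooled chi-square formula, with covariate adjustment treated as a reduction of N by the factor (1 − r-squared), an approach that reproduces the plan's other figures. The recurrence calculation that supports N = 600 stands.

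**What to change.** In section 9.1:

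- Replace 0.47 with 0.56.
- Replace .678 with .667.
- For recanalization, say how it differs from recurrence, state the platinum rate used and its source, and restate the detectable odds ratios for it: for example 0.60 to 0.56 at 33%, or 0.54 to 0.49 at 20.9%. Add a matching row to Table 5. If the two terms mean the same outcome, delete the sentence.

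The cost is a text edit. The first two changes make the stated figures more favourable. At any of the cited rates, the third makes them less so. Sample size, design and analysis are unaffected.

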9.2 Statistical Analysis Plan

9.2.1 Primary endpoints:

Chi-square tests (simple logistic regression) will be used to determine if rates of recurrence differ by coil type. Additionally, multiple logistic regression models will be used to examine those rates while adjusting for various covariates, including, but not limited to: site, age, gender, aneurysm size, neck size, packing density and rupture status. Models will be fit to examine potential interactions between covariates and randomization group in predicting outcomes; and final models will be fit depending on statistical and clinical significance of the covariates to the outcome as well as any change in the relationship between the randomization group and outcome. Analyses will be presented both as univariate and adjusted Odds Ratios and corresponding [Wald] 95% Confidence intervals.

While the study has been designed to minimize any missing data due to this being a longitudinal study, the potential for missing data or loss to follow-up is present. Patterns of missing data and dropout will be examined to determine if complete case analysis or available data analyses are appropriate or if imputation methods will need to be incorporated. Should a complete case analysis be appropriate, PROC LOGISTIC will be used to analyze these binary outcomes; otherwise PROC GLIMMIX will be used for an available data analysis. If imputation methods are called for, PROC MI and PROC MIANALYSE will be used and results presented. All analyses will be run at a type I error rate of 5% using SASv9.2, Cary, NC.

9.2.2 Secondary endpoints:

The rates of initial complete occlusion, partial occlusion, recanalization, retreatment, or hemorrhage from the target aneurysm during follow-up (and other binary outcomes) will be analyzed similar to the primary endpoints. Packing density will be analyzed by comparing means or medians (depending on the underlying distribution) between groups. Additionally, this will be compared using linear regression models (PROC REG or PROC MIXED, as above) adjusting for potential confounders including site, age, gender, aneurysm and neck size, and rupture status. Clinical outcomes and quality of life will be compared between groups using models appropriate for repeated measures (generalized linear mixed models). This will take into account changes in these outcomes over time as well as the 18-month evaluation and can accommodate some missing data as it does not require only complete cases be used but rather uses an available data analysis. Again univariate and multivariate results (means and 95% Confidence intervals) will be presented.

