5.3 Selection and Screening of Subjects

The study population for this clinical trial will be comprised of patients who have been diagnosed with intracranial aneurysms. In addition, these patients must satisfy all study inclusion and exclusion criteria. The trial will prospectively enroll and randomize up to 600 Subjects in a 1:1 ratio within only one stratification factor: participating site. The investigator or an approved member of the research team will review the patient's medical history for study eligibility and will fully inform any potential candidates about the purpose of the study. The difference between both types of coiling systems will be described and the potential risks and benefits will be explained in detail to each study candidate. Patients who voluntarily agree to participate in the trial will be asked to sign and date the Informed Consent Form (ICF). In the event a patient is unfit to provide signed informed consent (e.g. drowsy/confused), his/her Legally Authorized Representative (LAR) can sign the consent form. Once enrolled into the study, each participant will be assigned a study number. Patient names or identifiers will not be used on any study related documents. An electronic case report form (eCRF) will be completed at the end of each procedure and after each study related follow-up. Only the Principal Investigator of the study ([name]) and authorized members of the Sponsor including study monitors and auditors will have full access to the eCRF. Information from the eCRF will be entered into a secure, password protected study database. The Funder and its employees will have read-only access to collected eCRF study data, as provided by Northwestern, solely for review and adjudication of information related to any AE, SAE, ADE and UADE (as such terms are defined below) for legal and compliance purposes.

If a subject becomes pregnant while participating in this study, any angiographic follow-up will be done using non-contrast MRA as per standard of care.

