White et al. 2008 (HELPS)	Randomized Controlled trial	495 (249 randomized to the Hydrogel group)	Mean: 6.5 mm 2 - 4.9 mm: 42 5 - 9.9 mm: 144 10 - 24.9 mm: 63	139 vs. 110	-	47.3%	31.3% (near-complete)	21.4%	-
Gunnarsson et al. 2009	Retrospective	200	S (<10mm): 125 L (10 - 25 mm): 75	104 vs. 96	-	53.8%	29.6%	16.6%	58%

Table 2. Major Hydrogel coil studies - follow up results

Author and year	Complications/ Morbidity	Mortality	% followed up	Mean Follow-up (Months)	Recanalization	Retreatment
Berenstein et al. 2006	14 / 5.8% Immediate post-procedure Morbidity	0% (Immediate post-procedure)	51%	10.3	21%	-
Cloft et al. 2007 (HEAL)	10.9% (Immediate post-procedure)	-	135/191 (70.6%)	3-6	28.1%	-
Gaba et al. 2006	4%	2 (4.4 %)	84%	12.3	17%	10%
Deshaies et al. 2007	32.8%	-	90%	12	15%	-
Fanning et al. 2007	12% / 6.4% morbidity	1.1%	63%	7.5	14.3%	4.8%
Kang et al. 2007	16 procedure related-events	0%	68%	≥ 6 mo: 54 aneurysms ≥ 12 mo: 13 aneurysms	11%	-
White et al. 2008 (HELPS)	70 (Procedural Adverse events)	3.6%	-	-	-	-
Gunnarsson et al. 2009	15% complication (6% leading to permanent morbidity or mortality)	-	60.5%	16.3	21.5%	10.7%

Table 3. Hunt and Hess classification of SAH

Grade	Description
1	Asymptomatic, or mild H/A and slight nuchal rigidity
2	Cr. N. palsy (e.g. III, VI) moderate to severe H/A, nuchal rigidity
3	Mild focal deficit, lethargy, or confusion
4	Stupor, moderate to severe hemiparesis, early decerebrate rigidity
5	Deep coma, decerebrate rigidity, moribund appearance

Add one grade for serious systemic disease (e.g. HTN, DM, severe atherosclerosis, COPD) or severe vasospasm on arteriography.

Table 4. Schedule of assessment

HydroCoil Embolic System Clinical Trial	Screening & Baseline	Procedure	Post-procedure Follow-up	Immediate Follow-Up	Early Follow-Up	Final Follow-Up
Schedule of Events	Up to 30 days prior to surgery	Day 0	Day 1	3-28 Days	3-12 Months	18-24 Months
Review Inclusion/Exclusion	X					
Data Entry, Validation, Query Resolution	X	X	X	X	X	X
Obtain Informed Consent	X					
Randomization		X				
Adverse Events		X	X	X	X	X
Demographic Data	X					
Medical History	X					
Hunt & Hess Scale ¹	X	X	X			
Modified Rankin Score	X	X	X	X	X	X
NIH Stroke Scale (NIHSS) ¹	X	X	X		X	X
SF-36	X ³				X	X
Angiogram	X	X			X	X
MRA	X ²				X ²	X ²
Final Visit Assessment						X

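### Site is the only randomization stratum, but the first-listed primary test ignores it and the adjusted models leave its form and retention open: a minor, inexpensive improvement to section 9.2.1

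*Combined protocol and SAP*

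**What the plan says.** Section 5.3 sets up to 600 subjects in a "1:1 ratio within only one stratification factor: participating site". Section 5.2 allows up to 50 centers and expects at least 20 subjects from each. Block size is not given.

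Section 9.1 sizes the trial "using a two-sided two-sample test of proportions (Chi-square test", and Table 5 gives recurrence of 33.0% against 22.8% at N=600 and 80% power.

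Section 9.2.1 begins: "Chi-square tests (simple logistic regression) will be used to determine if rates of recurrence differ by coil type". It then adds multiple logistic models over an open list of covariates in which site is named. On model choice it states that "final models will be fit depending on statistical and clinical significance of the covariates to the outcome". The same sentence names a further criterion: how far a covariate shifts the estimated effect of coil type. The section does not say whether site enters as indicators, as a random effect or by conditioning, whether it must stay in, or how small sites are handled. The SAS procedure depends on the missing-data pattern: PROC LOGISTIC if complete cases are judged appropriate; "otherwise PROC GLIMMIX will be used for an available data analysis".

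**The concern.** When randomization is balanced within site, differences between sites cannot contribute to the difference between arms. The unstratified chi-square still counts them as noise, so it gives up a little power if sites differ. Some features of the protocol could make them differ: coiling follows local standards (section 6.6.1), and follow-up may be by catheter angiogram or MRA according to local practice (sections 6.9 and 6.10). Others could narrow the gap: one lesion class (section 5.3.2), a minimum operator experience (section 5.2) and core-lab grading (section 6.4), although section 6.4 has site investigators grading as well.

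The second part concerns pre-specification. The one factor built into the design can be dropped from the adjusted model after its influence on the treatment odds ratio has been seen. With up to 50 sites, the form in which it enters also changes the estimate. The stake is the choice of analysis and a few points of power, not the validity of the trial.

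**Working it through.** **The plan's own figure.** Inputs from section 9.1 and Table 5: 33.0% and 22.8%, 300 per arm, two-sided 5%. The pooled rate is (0.330 + 0.228)/2 = 0.279. The null standard error is √(2 × 0.279 × 0.721/300) = 0.03662. The alternative standard error is √(0.330 × 0.670/300 + 0.228 × 0.772/300) = 0.03638. Power is Φ[(0.102 − 1.96 × 0.03662)/0.03638] = Φ(0.831) = 79.7%. The odds ratio is (0.228/0.772)/(0.330/0.670) = 0.600. The stated 80% is reproduced.

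**Assumptions for the site question.** The documents give no between-site variance, so normal site effects on the log-odds scale were assumed, with SD 0, 0.3, 0.5 or 0.8 and the overall rates held at Table 5. At SD 0.8, 95% of sites would have platinum-arm recurrence of about 9% to 68%. The layouts are 30 sites of 20 (600/20 = 30, from section 5.2) and 50 sites of 12 (600/50 = 12), with exact 1:1 allocation within site. Missing outcomes are completely at random and equal in both arms. The studies in Table 2 followed 51% to 90%, so 30% missing lies within that experience. Each scenario had 100,000 replicates; the 95% Monte Carlo error is about 0.14 points for type I error and 0.25 for power.

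**Type I error of the chi-square.** With balance within site, the true variance is smaller than the one the test uses by a factor 1 − ρ, where ρ = var(site rate)/[p(1 − p)]. The approximate level is 2[1 − Φ(1.96/√(1 − ρ))].
- SD 0.5: var = 0.01116, so ρ = 0.01116/0.2211 = 0.050 and 1.96/√0.950 = 2.011, giving 4.4%. Simulation: 4.4-4.5%.
- SD 0.8: var = 0.02527, so ρ = 0.114 and 1.96/√0.886 = 2.083, giving 3.7%. Simulation: 3.7-3.9%.

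CMH by site stayed at 4.9-5.1%. Under simple randomization, without balance within site, the chi-square level was 5.0-5.1%, so the conservatism depends on balance.

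**Power, site-stratified CMH minus chi-square, in points.**

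| Layout | Missing | SD 0 | SD 0.3 | SD 0.5 | SD 0.8 |
|---|---|---|---|---|---|
| 30 × 20 | 0% | 0.0 | +0.5 | +1.3 | +2.9 |
| 50 × 12 | 0% | 0.0 | +0.5 | +1.2 | +2.9 |
| 45 unequal sites | 0% | −0.4 | +0.1 | +0.9 | +2.6 |
| 30 × 20 | 30% | −1.1 | −0.5 | +0.7 | +2.9 |
| 50 × 12 | 30% | −1.8 | −1.1 | 0.0 | +2.3 |
| 45 unequal sites | 30% | −2.1 | −1.5 | −0.2 | +2.2 |

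The unequal case assumes site sizes of 2 to 41 and blocks of 4. The losses arise because missing outcomes leave arms uneven within small sites. Strata with one arm only, no events or all events contribute nothing; they hold 7-14% of patients in the small-site layouts at 30% missing.

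**Form of site in the adjusted model.** With ordinary site indicators and 50 sites of 12, the median odds ratio was 0.572 for a true 0.600 with complete data. With 30% missing it was 0.556, with 93.0% coverage. In a separate run with 30 to 50 sites, indicators gave type I error of about 5.6-6.4%. Conditional logistic regression stayed within 0.004 of the true odds ratio, with coverage of 94.8-95.3%.

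**The case against.** The strongest reply is that nothing is broken. The chi-square holds its level, it is the test on which N=600 rests, and site is already a named covariate. The benefit depends on a between-site SD and a missing-data rate that the documents do not give, and its sign can be negative. All of this stands, and it is why the point is minor.

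A reader might infer that ignoring the randomization stratum inflates the type I error. It does not: with balance within site the error goes the other way. A reader might also infer that the plan declares the chi-square the sole primary test, or that it will fit 30-50 site indicators. It says neither. The first reading rests on order of listing and on the sizing; the second is only left open.

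Pooling small sites might seem an obvious companion to the CMH test, but it is not part of this recommendation. Pooling by site number gives strata that are not the randomization strata. It also cuts the complete-data gain at SD 0.8 with 50 sites of 12 from +2.9 to +1.4 points. The pooled odds ratio is no longer within-site: in large samples at SD 0.8, two-site strata give 0.583, between the within-site 0.564 and the marginal 0.600.

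**Conclusion.** The point holds as an optional improvement. The planned test is valid, and analysing by the stratum already used for randomization is modestly better if sites differ. The size is 0 to about +3 points of power with equal sites and complete data, against a loss of about 1 point (30 sites of 20) to 2 points (many small sites) when 30% of outcomes are missing and sites barely differ. These figures rest on assumed normal site effects with SD 0 to 0.8, balance within site and outcomes missing completely at random.

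The firmer gain is that site can no longer be dropped after its effect on the treatment odds ratio is known. It would go too far to say that the adjusted odds ratio then becomes fully pre-specified: the other covariates in section 9.2.1 remain selectable, and the form of site still follows the missing-data rule if that rule leads to PROC GLIMMIX.

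**What to change.** In section 9.2.1, replace the opening sentence with: 'The primary test is the Cochran-Mantel-Haenszel test of recurrence by randomized group, stratified by randomizing site, two-sided 5%, with the Mantel-Haenszel odds ratio and 95% CI. The unstratified chi-square is a sensitivity analysis.'

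Add: 'Site is kept in every adjusted model, whatever its p-value or its effect on the treatment odds ratio, by conditional logistic regression on site (STRATA in PROC LOGISTIC). Individual site indicators are not used. If the missing-data rule leads to PROC GLIMMIX, site is a random intercept, and the form of site then follows that rule.'

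If the sponsor wants to pool small sites, define the pooling before any outcome comparison by arm, and do not label the pooled odds ratio as within-site. If the sponsor keeps the chi-square as primary, the added text on adjusted models still applies.

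Cost: a protocol amendment, because the analysis plan is part of the protocol and section 8.2 requires IRB submission of changes before they take effect. N, data and software are unchanged. The statistical cost is the 1 to 2 points of power described above. The within-site odds ratio is also slightly further from 1 than the marginal one (0.585 against 0.600 at SD 0.5), so the report should state which is shown.

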8.2 IRB Approval

The Investigator or the study coordinator is responsible for submitting the study protocol and any changes issued by the Sponsor during the course of the study for IRB approval prior to any Subject enrollment and amendments taking effect as well as obtain renewals at periods determined by the IRB for the duration of the study.

9 Statistical Methods

Primary analysis of primary and secondary outcomes will be based on the intent-to-treat (ITT) principle. Secondary analyses will examine differences based on per protocol principles, as well as a detailed analysis of missing data, should there be any (see below).

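### Adjusting the recurrence odds ratio for packing density, measured after randomisation and a candidate mediator, means it no longer estimates the effect of assignment

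*Combined protocol and SAP*

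**What the plan says.** Section 9 sets the principle: "Primary analysis of primary and secondary outcomes will be based on the intent-to-treat (ITT) principle". Section 9.2.1 then gives the test of the primary endpoint: "Chi-square tests (simple logistic regression) will be used to determine if rates of recurrence differ by coil type". It continues: "Additionally, multiple logistic regression models will be used to examine those rates while adjusting for various covariates", the list being "including, but not limited to: site, age, gender, aneurysm size, neck size, packing density and rupture status". Final models depend on the statistical and clinical significance of the covariates "as well as any change in the relationship between the randomization group and outcome". On reporting: "Analyses will be presented both as univariate and adjusted Odds Ratios", with 95% Wald intervals.

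Section 9.1 also gives power for the adjusted analysis: "Using multiple logistic regression to predict recurrence (baseline rate in Platinum group of 33%), the sample of 600 patients would provide 80% power" for an odds ratio between 0.60 and 0.47, as the r-squared of the covariates with coil type runs from 0 to 0.2. It notes that "r-squared of 0 corresponds to hydrogel rate of 22.8% as in the univariate analysis".

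Other sections fix what kind of variable packing density is:

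- **6.3:** randomisation is done after the pre-coiling images are reviewed and just before coiling starts.
- **6.5:** packing density is total coil volume divided by aneurysm volume.
- **4.3:** it is a secondary outcome.
- **4.1:** hydrogel is hypothesised to raise it and to lower recanalization.
- **3.5:** the best-packed aneurysms are believed to be the best protected against recanalization.

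Section 9.2.2 models packing density as an outcome, adjusting for the other six variables. It also says that binary secondary outcomes are handled in a similar way to the primary endpoint.

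**The concern.** The numerator of packing density exists only once the assigned coils are in place, so it is a post-randomisation variable. Sections 4.1 and 3.5 together make it a candidate mediator: assignment may raise packing, and packing may lower recurrence. That is an inference from the protocol's rationale; the protocol does not state it as a mechanism.

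Conditioning on such a variable has two effects. Any part of the hydrogel effect that runs through packing is removed from the coil-type coefficient. And any unmeasured factor that affects both packing and recurrence becomes a source of bias in that coefficient, even if hydrogel does nothing. Neither has anything to do with baseline imbalance, which is the usual reason for adjustment.

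The model-selection rule makes this worse. A true mediator predicts the outcome and also shifts the treatment estimate, so it tends to meet both grounds for being kept. The reader would then see two odds ratios side by side, with no label saying that one is conditional on a consequence of treatment. They could disagree on significance for that reason alone. If the list carries over to the binary secondary outcomes, the same applies there.

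**Working it through.** **1. The plan's own figure.** Inputs from Section 9.1 and Table 5: 33.0% v 22.8%, 300 per arm, two-sided 5%.

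- Odds ratio = (0.228/0.772)/(0.33/0.67) = 0.60.
- Pooled rate = (0.33 + 0.228)/2 = 0.279. Null SE = √(0.279 × 0.721 × 2/300) = 0.0366. Alternative SE = √((0.33 × 0.67 + 0.228 × 0.772)/300) = 0.0364.
- Power = Φ((0.102 − 1.96 × 0.0366)/0.0364) = 79.7%. The stated 80% is reproduced.

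**2. What Section 9.1 already allows for.** Let packing density have SD 1 within arm and be d SD higher with hydrogel. Its r-squared with arm is (d²/4)/(1 + d²/4): 0.0625/1.0625 = 0.06 at d = 0.5, and 0.25/1.25 = 0.20 at d = 1. Multiplying n by (1 − r-squared) gives power of 77% and 70%. This is loss of precision only; the odds ratio stays at 0.60. The r-squared range in Section 9.1 covers this cost but not a shift in the odds ratio. (By the same formula the detectable recurrence odds ratio at r-squared 0.2 is 0.56, not the stated 0.47. That is a separate matter, and nothing here depends on it.)

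**3. Mediation.** Model: logit P(recurrence) = b0 + (1 − f)·T·arm + (f·T/d)·M. M is packing density, f is the share of the log odds ratio that runs through it, and b0 and T are solved so that the arm rates stay at 33.0% and 22.8%. The adjusted odds ratio is exp((1 − f)·T). Power comes from 20,000 simulated trials per cell (Monte Carlo SE at most 0.4 points). Chi-square power is 79–80% throughout.

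| Arm shift d | Share f | Recurrence OR per SD of packing | Adjusted OR | Power, adjusted |
|---|---|---|---|---|
| 0.5 SD | 0 | 1.00 | 0.60 | 77% |
| 0.5 SD | 25% | 0.77 | 0.68 | 53% |
| 0.5 SD | 50% | 0.58 | 0.76 | 29% |
| 0.5 SD | 75% | 0.42 | 0.86 | 11% |
| 1 SD | 0 | 1.00 | 0.60 | 70% |
| 1 SD | 25% | 0.88 | 0.68 | 47% |
| 1 SD | 50% | 0.77 | 0.77 | 24% |
| 1 SD | 75% | 0.67 | 0.88 | 10% |

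The 0.5 SD, 75% row needs a very strong packing effect, and the conclusion does not rest on it.

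**4. Conflict between the two tests, if packing density stays in the model.** Chi-square is significant and the adjusted test is not in 26% (0.5 SD) or 33% (1 SD) of trials at f = 25%, and in 51% or 56% at f = 50%. With no mediation the rates are about 4–5% and 12%.

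**5. Would the selection rule keep it?** The plan gives no thresholds; assume p < 0.05 for packing density and a change of more than 10% in the odds ratio.

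- Either criterion suffices: kept in 82% (0.5 SD) or 64% (1 SD) at f = 25%, and 100% or 96% at f = 50%, against 6% or 27% with no mediation.
- Both required: about 70% or 30% at f = 25%, and 100% or 80% at f = 50%.
- Conflict and retention together at 1 SD, f = 25%: 29% (either) or 16% (both).

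**6. No hydrogel effect, but an unmeasured common cause of packing and recurrence.**

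- Correlation 0.3 with packing and odds ratio 2 per SD on recurrence: adjusted odds ratio 0.91 (0.5 SD) or 0.82 (1 SD) if the factor raises both. If it raises packing and lowers recurrence (odds ratio 0.5 per SD), 1.10 or 1.21. False-positive rate about 8% or 16% with either sign, against 5% for chi-square.
- Weaker factor (correlation 0.2, odds ratio 1.5): 0.96 or 0.93 when it raises both, with false-positive rates of about 5% and 7%.

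**The case against.** **The main inference is untouched.** The wording of Section 9.2.1, the intention-to-treat principle and Table 5 all point to the unadjusted test, and its odds ratio is reported too. This stands, and it limits the point to the interpretation of the adjusted odds ratio. Still, no section formally names the chi-square test as decisive, and Section 9.1 gives power for the adjusted model, so that odds ratio is not incidental.

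**Packing density is only a candidate and may drop out.** True. Requiring both selection criteria lowers retention at modest mediation, as step 5 shows. But the rule tends to keep packing density where the distortion is larger, under either reading.

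**The illustration is loosely anchored.** Also fair. Section 3.5 quotes mean packing of 73% v 32%, but for first-generation coils, with 11 aneurysms per group, historical controls and no SD. Section 6.5 does not say whether the coil diameter is dry or expanded. The measured shift could therefore lie outside 0.5–1 SD. The confounder in step 6 must also be residual to aneurysm size, neck size, rupture status and site, which are already on the list; with the weaker factor the false-positive inflation is small. These points affect the size of the problem. They do not change what the adjusted odds ratio estimates.

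**Carry-over to the secondary outcomes is not explicit.** Agreed. Section 9.2.2 does not restate the list for them, so it is a possibility to close off.

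**Conclusion.** The concern holds. A recurrence odds ratio adjusted for packing density does not estimate the total effect of assignment, and the plan does not label it as anything else. The post-randomisation status follows directly from Sections 6.3 and 6.5; the mediator status is inferred from Sections 3.5 and 4.1.

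The size cannot be fixed from the documents. Across assumed arm shifts of 0.5–1 SD and mediated shares of 25–50%, a true odds ratio of 0.60 appears as 0.68–0.77, and power falls from about 80% to 24–53%. If packing has no bearing on recurrence and shares no unmeasured cause with it, the adjusted odds ratio is unchanged and only precision is lost. The chi-square test, its odds ratio and the sample size are unaffected. This should be fixed, but it does not undermine the primary test.

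**What to change.** 1. Delete packing density from the covariate list in Section 9.2.1, and state that it is also excluded from the adjusted models for the binary secondary outcomes.
2. Use the pre-randomisation variables that Section 9.2.2 already names (site, age, gender, aneurysm size, neck size, rupture status) as the adjustment set.
3. Report any model containing packing density as an exploratory mediation analysis, with its no-confounding assumptions stated, and not as an adjusted treatment effect.

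Two further changes are worth making, though the point does not depend on them: state that the unadjusted intention-to-treat chi-square test decides the primary endpoint, and prespecify the adjustment set with no selection on change in the treatment estimate.

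The cost is a change of wording in the analysis plan. No extra data or patients are needed, and the mechanistic question is kept.
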